9.5. Outliers

Identification of doubtful data and data not suitable to analysis can be performed by visual analysis of dispersion diagrams, boxplots, etc.

9.6. Population for analysis

The following populations will be used for analysis:

1. All enrolled patients (Intent-to-treat, ITT).
2. Safety population: Patients who received at least one infusion, according to the prescribed treatment.

9.7. Statistical methods

The methods of statistical analysis will depend on the type of source data and the type of distribution. The possibility of using a number of statistical methods will be evaluated after collection of the data, since the nature of distribution, homogeneity of the sample, and other parameters are unknown at the beginning of the study.

The list of methods may be expanded during the analysis for high-quality data processing.

9.7.1. Assessment of demographic indicators and baseline data

The categorical (qualitative) data will be described with incidences, percentage, or proportions, and 95% confidence interval for percentage or proportions.

The interval (quantitative) data will be described with arithmetic mean, standard deviation, median, minimum, maximum, lower quartile (25%) and higher quartile (75%), coefficient of variation, and 95% confidence interval for the mean.

Shapiro-Wilk test will be used to test normality of the distribution.

9.7.2. Statistical methods for efficacy analysis

ITT will be the main population for efficacy analysis.

9.7.2.1. Analysis of the Primary Efficacy Endpoint

The primary efficacy outcome for the first part of the study is 'Clinical status of the patient (according to 7-point ordinal scale) on day 15'. Because there is uncertainty about the clinical course and potential different trajectories according to baseline disease severity, the day of the primary endpoint may be modified based on a blinded evaluation of various timepoints (e.g., days 7-17). Analyses will be evaluated by baseline severity (mild/moderate vs severe). For example, in mild disease, recovery may occur rapidly such that all patients with mild disease have resumed normal activities by Day 15. Hence, the final timepoint selected may vary accordingly.

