4. STUDY DESIGN

4.1. Primary and Secondary Outcomes

According to the aim and objectives of this study, safety and efficacy of Polyoxidonium®, lyophilizate for solution for injections and topical application, 6 mg (NPO Petrovax Pharm LLC, Russia) will be evaluated in hospitalized patients with coronavirus disease (COVID-19).

Efficacy outcomes

Primary efficacy outcome

Subject clinical status using the WHO 7-point ordinal scale on day 15 as compared to baseline.

1. Not hospitalized, no limitations on activities.
2. Not hospitalized, limitation on activities.
3. Hospitalized, not requiring supplemental oxygen.
4. Hospitalized, requiring supplemental oxygen.
5. Hospitalized, on non-invasive ventilation or high flow oxygen devices.
6. Hospitalized, on invasive mechanical ventilation or ECMO.
7. Death.

Secondary efficacy outcomes

Clinical severity assessed by scales

1. Subject clinical status using the WHO 7-point ordinal scale

- Time to improvement of each parameter of the primary scale from admission.

- Subject clinical status at days 3, 5, 8, 11, and 29.
 - Average change in the clinical status at days 3, 5, 8, 11, 15, and 29 as compared to baseline.
2. *The NEWS Score (National Early Warning Score) describes the vital signs (pulse rate, breathing rate, temperature, blood pressure etc.) and its deviation from the reference ranges):* is evaluated daily and on day 15.
- The time to discharge or to a NEWS of ≤ 2 and maintained for 24 hours, whichever occurs first.
 - Change from baseline to days 3, 5, 8, 11, 15, and 29 in NEWS.
3. *Oxygenation, including mechanical ventilation:*
- Change (day by day) in the need for oxygenation in the first 28 days (up to day 29).
4. *Hospitalization*
- Duration of hospitalization (days).
5. *Mortality (date, cause)*
- 28-day mortality.
6. *SOFA scale (evaluation of organ failure associated with sepsis):* is evaluated daily and on day 15.
- Change from baseline to days 3, 5, 8, 11, 15, and 29 in SOFA.

Safety outcomes

Safety outcomes

- Cumulative incidence of serious adverse events/reactions (SAEs, SARs)
- Cumulative incidence of adverse events/reaction (AEs, ARs)
- Permanent or temporary discontinuation of infusions/injections (by any cause)
- Clinically significant changes in the levels of leukocytes, haemoglobin, platelets, creatinine, glucose, total bilirubin, ALT, AST, CRP, and other parameters.

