4.2. Type/design of the study

This study is an open multi-centre observational study evaluating the efficacy and safety of a non-interventional drug.

The design of a non-invasive non-interventional study was chosen to evaluate the efficacy of the drug in routine clinical practice. Since this study will be non-interventional, all procedures will be carried out in strict accordance with the standards of routine clinical practice and meet the non-interventional criteria set by the Good Pharmacovigilance Practice of the Eurasian Economic Union [approved by the decision of the Council of the Eurasian Economic Commission dated 03.11.2016 No. 87].

No	CRITERION	CONTENT
1	Object, MA	Drug products approved for human use; with a valid marketing authorization
2	Rationale for prescription	As judged by the doctor within the routine clinical practice
3	Time of prescription	Prior to inclusion in the study and regardless of the decision to participate
4	Requirements to the prescription	According to the approved therapeutic indications (therapeutic indications, dosage, etc.)

According to the current routine practice, up-to-date and widely accepted

5	Patient management	clinical guidelines and guides According to the protocol, however, the intervention in the routine management of the patient is minimal
6	Randomization, blinding	Not applicable

The clinical efficacy will be assessed by changes in the patient’s clinical status, duration of hospitalization, oxygenation/mechanical ventilation. The clinical examination will include clinical, laboratory, and instrumental investigations according to the current guidelines on treatment of COVID-19 in the Russian Federation. No additional procedures, except for the special scales (non-invasive), will be carried out during the planned non-interventional study.

The overall objective of the study is to evaluate the clinical efficacy of the investigational product in adult patients hospitalized with COVID-19. The primary endpoint is the patient’s clinical status (in a 7-point ordinal school) on day 15 in accordance with the WHO Master Protocol¹.

The study will be conducted in the clinical centre during hospitalization and outpatient visits of patients to the clinical centre, if necessary.

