Patients who meet the inclusion criteria and do not meet any of the exclusion criteria will be included in a single study group, that will receive Polyoxidonium®, lyophilizate for solution for injections and topical application, 6 mg (NPO Petrovax Pharm LLC, Russia) in dose of 12 mg once daily intravenously (IV) for 3 days, then every other day intramuscularly (IM) on days 5–17 (the total treatment course is 10 injections).

The data collected in this observational program should help doctors find more effective therapy for other patients with COVID-19.

The study will include the following periods:

- **Treatment period** (17 days in total, days 1...17, if the study criteria are met) with administration of the investigational product (IP) (intravenous injections for 3 days, then intramuscular injections for 14 days), assessment of the clinical status, recording of AEs.

- **Follow-up period** (days 18...29±3)

Figure 4.1 shows the study flow chart.

[figure not shown]

Figure 4.1. Study flow chart

¹ MASTER PROTOCOL. A Multi-centre, Adaptive, Randomized, Double-Blind, Placebo-Controlled Clinical Trial of the Safety and Efficacy of Investigational Therapeutics for the Treatment of COVID-19 in Hospitalized Patients. Electronic source Free access: <https://www.who.int/blueprint/priority-diseases/key-action/multicenter-adaptive-RCT-of-investigational-therapeutics-for-COVID-19.pdf>. Access date: March 13, 2020

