4.3.1. Blinding

In contrast to interventional clinical trials, the design of non-interventional trials does not involve randomization and blinding. In accordance with the non-intervention principle, the doctor's decision to prescribe a therapy is made before the patient is included in the study as part of routine clinical practice and in no way can be associated with the possibility of the patient participating in this study. As a result, blinding is impossible. The procedures will be carried out within the current routine clinical practice in the presence of relevant therapeutic indications.

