Visits to the clinic are preferred after discharge, but the quarantine or other reasonable factors can limit this opportunity. The visits could be performed in a form of phone call or with other remote communication technologies. Some data will not be collected by obvious reasons.

- Evaluation of the measures of clinical support.
- Assessment of the clinical status according to the 7-point ordinal scale — every day during hospitalization up to and including Day 17.
- Assessment of the clinical status according to the NEWS scale and SOFA scale.
- Oropharyngeal/nasal (OP/N) sample.
- Haematology.
- Blood chemistry.
- Urinalysis.
- Administration of the investigational product.
- Physical examination (including lung auscultation).
- Collection of the efficacy data (oxygenation, mechanical ventilation, prolongation of hospitalization).
- Collection of information about concomitant treatments.
- Recording of AEs.

Follow-up period

(Day 29±3)

Full list of the procedures is provided in Appendix 1.

The visits are performed in the in-patient settings. If the patient is discharged earlier, the procedures will be performed within the outpatient visits to the clinic (if possible).

- Evaluation of the measures of clinical support — only if the hospitalization is prolonged.
- Assessment of the clinical status according to the 7-point ordinal scale.
- Assessment of the clinical status according to the NEWS scale and SOFA scale.
- Oropharyngeal/nasal (OP/N) sample.
- Haematology.
- Blood chemistry.
- Urinalysis.
- Collection of the efficacy data (oxygenation, mechanical ventilation, prolongation of hospitalization).
- Collection of information about concomitant treatments.
- Physical examination (including lung auscultation).
- Recording of AEs.

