7. ASSESSMENT OF EFFICACY AND PHARMACODYNAMIC EFFECTS

7.1. Efficacy outcomes

According to WHO Master Protocol, the primary endpoint will be evaluated on day 15 of the first part of the study. The day of the primary endpoint may be modified based on a blinded evaluation of various days because there is uncertainty about the clinical course and potential different trajectories according to baseline disease severity¹.

Efficacy outcomes

Primary efficacy outcome

Subject clinical status using the WHO 7-point ordinal scale on day 15 as compared to baseline.

6. Not hospitalized, no limitations on activities.
7. Not hospitalized, limitation on activities.
8. Hospitalized, not requiring supplemental oxygen.
9. Hospitalized, requiring supplemental oxygen.
10. Hospitalized, on non-invasive ventilation or high flow oxygen devices.
11. Hospitalized, on invasive mechanical ventilation or ECMO.
12. Death.

Secondary efficacy outcomes

Clinical severity assessed on scales

1. Subject clinical status using the WHO 7-point ordinal scale

- Time to improvement of each parameter of the primary scale from admission.
- Subject clinical status at days 3, 5, 8, 11, and 29.
- Average change in the clinical status at days 3, 5, 8, 11, 15, and 29 as compared to baseline.

2. The NEWS Score (National Early Warning Score) describes the vital signs (pulse rate, breathing rate, temperature, blood pressure etc.) and its deviation from the reference ranges): is evaluated daily and on day 15.

- The time to discharge or to a NEWS of ≤ 2 and maintained for 24 hours, whichever occurs first.
- Change from baseline to days 3, 5, 8, 11, 15, and 29 in NEWS.

3. Oxygenation, including mechanical ventilation:

- Change (day by day) in the need for oxygenation in the first 28 days (up to day 29).

4. Hospitalization

- Duration of hospitalization (days).

5. Mortality (date, cause)

- 28-day mortality.

6. SOFA scale (evaluation of organ failure associated with sepsis): is evaluated daily and on day 15.

- Change from baseline to days 3, 5, 8, 11, 15, and 29 in SOFA.

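### The primary-endpoint day may be moved after a blinded evaluation that an open, single-group study cannot provide, so the day can be chosen with the results in view

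*Combined protocol and SAP*

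**What the plan says.** Sections 4.1 and 7.1 define the primary outcome as status on the WHO 7-point ordinal scale on Day 15 compared with baseline. Section 7.1 then says: "The day of the primary endpoint may be modified based on a blinded evaluation of various days". Section 9.7.2.1 says the same and gives an example range: "the day of the primary endpoint may be modified based on a blinded evaluation of various timepoints (e.g., days 7-17"). The reason offered is that the clinical course is uncertain and may differ by baseline severity. After an example about mild disease, the section ends: "Hence, the final timepoint selected may vary accordingly". It writes no rule of one day per severity stratum.

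On design, section 4.2 says "This study is an open multi-centre observational study" and that eligible patients "will be included in a single study group". Section 4.3.1 says "As a result, blinding is impossible", and section 4.3.2 marks randomization as not applicable.

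On data, section 6.2 plans the 7-point score "every day during hospitalization up to and including Day 17". Section 4.1 lists as a secondary outcome: "Average change in the clinical status at days 3, 5, 8, 11, 15, and 29 as compared to baseline". Section 9.8 sets a 5% significance level. Sections 9.1 and 9.7.2.1 name no test for the primary endpoint.

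**The concern.** A blinded review of pooled data can protect the choice of a primary day in a randomized, masked trial, because pooled outcomes do not show the difference between arms. Here there are no arms. The primary result is the change in the one treated group, and the pooled outcome by day shows exactly that. Anyone who carries out the evaluation has seen the result for every day from which they may choose.

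The study's only primary endpoint could therefore be placed on the most favourable day. A 95% interval or a 5% test computed on a day chosen in this way would not have its nominal error rate, and the estimated change would be biased towards improvement. The text permits this; nothing suggests that it is intended.

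**Working it through.** **1. Do the passages fit together?**

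- Permission to move the day: sections 7.1 and 9.7.2.1. Neither gives a criterion, deadline, data cut-off or decision-maker.
- The only safeguard named is a blinded evaluation, which is not defined anywhere.
- Conditions for that safeguard: none are met. The study is open with one treated group (4.2), blinding is impossible (4.3.1) and there is no randomization (4.3.2).
- Other controls: section 11.7 requires written, approved amendments, and ethics approval for changes that affect scientific value, but does not require approval before outcomes are seen. Because the protocol already grants the permission, a change of day might not be treated as an amendment at all. Section 9.3 asks only that changes of method be justified in the final report, and section 9.7 leaves the choice of methods until after data collection.

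Nothing in the documents closes the gap.

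**2. How many days are candidates?** Days 7 to 17 inclusive: 17 - 7 + 1 = 11. Scores are planned daily in hospital to Day 17, so up to 11 days could be inspected. The change-from-baseline days listed in section 4.1 that fall in the range are 8, 11 and 15: three days.

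**3. How far could the error rate move?** The plan states no figure to reproduce: no primary test, standard deviation or correlation. From the documents come n = 50 (the stated minimum), the 5% level and the days. Assumed: a two-sided test, no true change, normal daily values with correlation ρ^|i-j| between days i and j, and always choosing the most favourable day.

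For each day d, the change is Y_d - Y_1 and t_d = mean change / (SD of change / √50). A study counts as favourable if any candidate day shows improvement with two-sided p < 0.05. Each setting used 20,000 simulated studies, with one shared Day 1 baseline:

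| ρ | Best of Days 7-17, favourable | Best of Days 7-17, either direction | Best of Days 8, 11, 15, favourable |
|---|---|---|---|
| 0.5 | 0.132 | 0.266 | 0.060 |
| 0.7 | 0.114 | 0.226 | 0.059 |
| 0.9 | 0.089 | 0.176 | 0.053 |
| 0.95 | 0.077 | 0.161 | 0.051 |
| 0.98 | 0.080 | 0.157 | 0.049 |

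With Day 15 fixed, the favourable rate is 0.024-0.026 (nominal 0.025) and the rate in either direction 0.047-0.053 (nominal 0.05). A repeat of these simulations with a different random seed agreed within simulation error.

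If the daily test statistics themselves follow the AR(1) pattern, without a shared baseline, the best of 11 days gives 0.054-0.207 favourable and 0.108-0.389 in either direction over the same correlations. The independence bound for 11 tests is 1 - 0.95^11 = 0.431.

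**4. How far could a descriptive figure move?** Assume a constant discharge rate h per day, so that the share discharged by day d is 1 - exp(-h·d):

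| h | Day 15 | Day 17 | Gain (points) |
|---|---|---|---|
| 0.05 | 0.528 | 0.573 | 4.5 |
| 0.08 | 0.699 | 0.743 | 4.5 |
| 0.12 | 0.835 | 0.870 | 3.5 |

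Moving the day earlier lowers the share.

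**5. What would fixing the day leave unsolved?** With no drug effect, a natural improvement of 0.5 scale points and an assumed SD of 1.5, a test at n = 50 rejects no change with probability Φ(0.5·√50/1.5 - 1.96) = Φ(0.397) = 0.65.

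**The case against.** The strongest objection is that the choice of day hardly matters in this study. Hospitalized patients tend to improve over 7-17 days whatever they receive, so a before-after test is likely to be significant on any day. In simulations with no drug effect, using the discharge rates above, assumed death rates of 0.003-0.01 per day and patients starting equally at scores 3 and 4, a fixed Day 15 test was already significant in 71-100% of studies. The best of Days 7-17 was significant in 82-100%. The gain from choosing was 0-11 points, and under 1 point in six of nine settings. This stands, and it limits what the fix can achieve. It does not justify leaving the primary endpoint open, because an estimate reported with an interval is also biased if its day was picked on the result.

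The no-change null, the normal model and the always-best choice are also unfavourable assumptions. That is fair, and section 3 of the working should be read as an illustration. At correlations of 0.9 or more, the favourable figure is about 8-9%.

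Eleven candidate days may be generous, because daily scoring is tied to hospitalization and contact after discharge may be remote. With only Days 8, 11 and 15 the rate still roughly doubles, to 5-6%.

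Day 15 change is also a listed secondary outcome, so it should still be reported. That makes a switch visible but does not stop another day from being labelled primary.

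Finally, an evaluator could in principle be kept from the outcome data. The text describes an evaluation of various timepoints, with no such restriction and no other definition.

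**Conclusion.** The concern holds. The plan lets its only primary endpoint be moved under a safeguard that its own design rules out. Under the stated assumptions (n = 50, no true change, paired t-test, correlation 0.5 to 0.98), choosing the best of Days 7-17 raises the chance of a falsely significant improvement from 2.5% to about 8-13%; choosing among Days 8, 11 and 15 raises it to about 5-6%. The correlations, test, null and discharge rates are assumptions, since the documents give none of them.

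The conclusion rests on the contradiction in the text and not on these figures. It should be corrected because the safeguard is wrong as written and the repair is simple. Fixing the day removes the selection problem only; without a control group, the result still would not separate a drug effect from natural recovery.

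**What to change.** - **Section 7.1:** delete the sentence that allows the primary day to be modified.
- **Section 9.7.2.1:** delete the clause that allows modification and the closing sentence that lets the final timepoint vary.
- **Both sections:** state that Day 15 is the primary day for all patients and for both severity strata.
- **If another day is wanted for mild or moderate disease:** name it in an amendment approved before any outcome data are reviewed.
- **Other days:** report Days 3, 5, 8, 11 and 29, and any other daily scores, as descriptive.

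Two related details should be settled at the same time: Table 1 gives Day 15 a window of ±1 day, and section 6.3.8 records the worst score of the previous day. The text should say which score counts as Day 15.

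The cost is protocol and SAP wording only. The sponsor gives up the freedom to move the day if most mild patients have recovered by Day 15; the listed earlier days would still show that recovery.

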9.7.2.2. Analysis of the secondary efficacy endpoints

The interval (quantitative) data will be described with arithmetic mean, standard deviation, median, lower quartile (25%) and higher quartile (75%), minimum, maximum, coefficient of variation, and 95% confidence interval for the mean. The categorical (qualitative) data will be described with incidences, percentage, or proportions, and 95% confidence interval for percentage or proportions.

The time to event data will be processed via survival analysis with the use of Kaplan-Meier curves and 95% confidence intervals.

The following standard parametric tests are planned for comparison of quantitative data with normal distribution: Student t-test for dependent/independent samples, analysis of variance (ANOVA) for repeated measurements.

The following standard non-parametric tests are planned for comparison of quantitative data with distribution other than normal: Mann-Whitney U-test, Wilcoxon T-test, Friedman test.

Shapiro-Wilk test will be used to test normality of the distribution.

The incidences will be compared between the treatment groups with Pearson's χ^2 -test or Fischer's exact test.

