Open multi-centre observational study of efficacy and safety of a medicinal

	
product.
 
The clinical efficacy will be assessed by changes in the patient's clinical status, duration of hospitalization, oxygenation/mechanical ventilation. The clinical examination will include clinical, laboratory, and instrumental investigations according to the current guidelines on treatment of COVID-19 in the Russian Federation.

POPULATION	Hospitalized patients of 18 years and older with confirmed COVID-19.
SAMPLE SIZE	At least 50 patients
TREATMENT ALLOCATION	All study subjects will receive treatment with Polyoxidonium, lyophilizate, 12 mg, in addition to the standard treatment
DIAGNOSIS	Verified COVID-19

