5. SCREENING AND WITHDRAWAL OF THE SUBJECTS

5.1. Inclusion criteria

1. The patient is already receiving, or the patient have been prescribed therapy with Polyoxidonium® in accordance with the approved labelling in combination with COVID-19 therapy recommended by the Ministry of Health of the Russian Federation.
2. Verified diagnosis: COVID-19.
3. Severity of the disease at hospitalization:
 - severe disease: requiring mechanical ventilation or oxygen, a $SpO_2 \leq 94\%$ on room air or tachypnoea (respiratory rate ≥ 24 breaths/min).
 - mild-moderate disease: $SpO_2 \geq 94\%$ and respiratory rate ≤ 24 breaths/min without supplemental oxygen.
4. Patients who signed the informed consent.
5. Understands and agrees to comply with planned study procedures.
6. Age ≥ 18 years old at the enrolment.
7. Has laboratory-confirmed SARS-CoV-2 infection as determined by PCR, or other commercial or public health assay in any specimen prior to the enrolment.

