9.4. Drop-outs, withdrawn patients, and missing data

No missing data will be substituted. The missing/omitted data will not be considered during statistical analysis.

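### The plan does not say how deaths enter the two time-to-recovery endpoints; if they are censored in the Kaplan-Meier analysis, recovery is overstated

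*Combined protocol and SAP*

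**What the plan says.** Section 4.1 lists two secondary endpoints that are times to a favourable event: "Time to improvement of each parameter of the primary scale from admission" and "The time to discharge or to a NEWS of ≤ 2 and maintained for 24 hours, whichever occurs first". The method for time-to-event data is one sentence, repeated in the synopsis, Section 9.1 and Section 9.7.2.2: "The time to event data will be processed via survival analysis with the use of Kaplan-Meier curves and 95% confidence intervals".

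Death is an anticipated outcome. It is level 7 of the ordinal scale, and "28-day mortality" is a separate secondary endpoint, with date and cause recorded. Section 5.1 admits patients with "severe disease: requiring mechanical ventilation or oxygen", alongside patients with mild to moderate disease.

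No section gives a censoring rule, a competing-risk method or any other treatment of death for these two endpoints. The nearest text is Section 9.4: "No missing data will be substituted. The missing/omitted data will not be considered during statistical analysis". It concerns missing values and does not mention deaths. The planned sample size is "At least 50 patients", all in one group (Section 4.2).

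**The concern.** A patient who dies before improving, or before discharge or a sustained low NEWS, can no longer have that event. Kaplan-Meier assumes that a censored patient keeps the same future chance of the event as those still under observation. Censoring at death therefore credits the dead with the recovery rate of the survivors. One minus the Kaplan-Meier estimate then exceeds the proportion who actually recovered, and the median is reached too early.

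There is no control arm whose curve would carry a similar error. The quantity reported is an absolute recovery curve, so the bias passes straight into it, and it always favours recovery. Because the rule is unwritten, it could also be chosen after the deaths are known.

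**Working it through.** **Nothing to reproduce.** The documents give no expected recovery rate, mortality or event count for these endpoints, and no derivation of the sample size. The check therefore runs over assumed values.

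**Inputs.** The horizon of 28 days comes from Section 4.1. R is the true proportion with the recovery event by Day 28, and D is the true proportion dying before that event. Both are assumptions.

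**Model.** Cause-specific hazards are constant and there is no other censoring.

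- Total cumulative hazard: L = −ln(1 − R − D).
- Share belonging to recovery: L × R/(R + D).
- One minus Kaplan-Meier with deaths censored: 1 − exp(−L × R/(R + D)).
- The Aalen-Johansen cumulative incidence returns R itself.

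**One case in full.** With R = 0.70 and D = 0.10, L = −ln(0.20) = 1.609. The recovery share is 1.609 × 0.70/0.80 = 1.408. One minus Kaplan-Meier is 1 − exp(−1.408) = 0.755, against a true 0.70, an excess of 5.5 points.

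**All cases** (one minus Kaplan-Meier, with the excess in percentage points):

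| D | R = 0.60 | R = 0.70 | R = 0.80 |
|---|---|---|---|
| 2% | 0.608 (0.8) | 0.710 (1.0) | 0.812 (1.2) |
| 5% | 0.621 (2.1) | 0.726 (2.6) | 0.832 (3.2) |
| 10% | 0.644 (4.4) | 0.755 (5.5) | 0.871 (7.1) |
| 20% | 0.701 (10.1) | 0.833 (13.3) | not computable (R + D = 1) |

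At R = 0.90 the excess is 1.5 points for D = 2% and 4.1 points for D = 5%.

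**Median time to recovery.** With deaths as competing events it is −(28/L) × ln(1 − 0.5(R + D)/R). With deaths censored it is 28 × ln 2 divided by the recovery share.

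- R = 0.70, D = 0.10: 14.7 days against 13.8 days.
- R = 0.70, D = 0.20: 12.5 days against 10.8 days.

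**Check at 50 patients.** Event days were drawn uniformly over days 3 to 27, with 500 replicates per setting and everyone else followed to the end.

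- 35 recoveries and 5 deaths: mean 0.753 against a true 0.70.
- 35 recoveries and 10 deaths: mean 0.827 against 0.70.
- Deaths kept in the risk set to Day 29: exactly 0.70 in both.

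**Dependence on timing.** With 35 recoveries and 10 deaths, suppose every death precedes every recovery. Then 40 patients remain at risk and the estimate is 35/40 = 0.875. If every death follows the last recovery, the estimate is 35/50 = 0.70 and there is no bias. The simulated means sit between such extremes.

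**The case against.** **Deaths are not stated to be censored.** A reader might infer that the plan prescribes censoring at death, or that Kaplan-Meier is itself the error. Neither is supported. The plan names the estimator and is silent on deaths. Holding deaths as non-events to Day 29 would still be a Kaplan-Meier calculation, and with no other censoring it would be unbiased. The gap is the missing rule. It matters because censoring at death is the conventional default.

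**Methods may be changed.** Sections 9.3 and 9.7 allow methods to be replaced or added. That permits a correction, but names none, and a choice made once the deaths are known is not prespecified.

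**The endpoints are secondary.** A reader might take these curves for the study's main efficacy result, or conclude that its efficacy conclusion is invalid. The documents do not support that. The primary endpoint is ordinal status on Day 15, with death as a scored level, and 28-day mortality is reported separately, so deaths stay visible. No comparison of these curves with outside data is planned. This objection stands and limits the importance of the point.

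**The bias may be small.** This stands in part. Mild to moderate disease is eligible, patients must sign consent, and renal failure is excluded, so low mortality is plausible. At 80% recovery in 50 patients, the 95% interval half-width is about 1.96 × √(0.8 × 0.2/50) = 11 points, well above the bias at 2% to 5% mortality. Severe patients are eligible too, however, and sampling error has no fixed direction whereas this bias does.

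**Not every death competes.** This is also correct. A patient who improves, or reaches a sustained low NEWS, and later dies has had the event. The composite endpoint cannot occur later than discharge. D therefore means mortality before the event, which may be lower than 28-day mortality.

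**Conclusion.** The concern holds as an omission. Kaplan-Meier is the only named method for two endpoints that death can preclude, and the handling of death is not specified. If deaths are censored while recoveries are still to come, the upward direction of the error is certain. Its size is not, because it depends on mortality before the event and on when deaths fall.

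Over assumed recovery of 60% to 80% with constant hazards, the excess at 28 days runs from about 1 point at 2% mortality to 4 to 7 points at 10%. At 20% it is 10 to 13 points, for recovery of 60% to 70%. It is negligible in a mostly mild cohort and material in a severe one. Two secondary, descriptive endpoints are affected; the primary endpoint and the sample size are not. The change should be made, but it does not undermine the study as a whole.

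**What to change.** In Sections 9.1 and 9.7.2.2 and the synopsis, state that time to improvement and time to discharge or NEWS of 2 or less for 24 hours will be estimated by Aalen-Johansen cumulative incidence with 95% confidence intervals. Death before the event is a competing event; withdrawal and loss to follow-up are censored. Add that a death in hospital does not count as a discharge.

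Holding deaths as non-events to Day 29 gives the same estimate only if no one is otherwise censored earlier. Section 5.3 provides for withdrawal and loss to follow-up, so Aalen-Johansen should be the named method. Kaplan-Meier may be kept for time to death if 28-day mortality is analysed that way.

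The cost is one or two sentences in three places. Date of death is already recorded under Section 4.1, and the estimator is available in R and SAS, both named in Section 9.2. No new data are needed.
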